## 1.0 SUMMARY OF STUDY

The present study proposes to study the effect of a single preoperative dose of baclofen on pain treated in the first 24 hours after kidney stone-related surgeries using a placebo-controlled, double-blind methodology. Because this patient population often has a history of significant opioid use, which would be expected to alter postoperative pain medication requirements, patients will be stratified into those which would be expected to be opioid tolerant (use >30 OME daily) and those who are generally opioid naïve.

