### **3.0 OBJECTIVE(S) & HYPOTHESIS**

Purpose of study:

To determine whether a single, oral dose of baclofen alters postoperative opioid requirements

Study Hypothesis:

We hypothesized that a single, oral dose of baclofen given to patients undergoing kidney stone surgery will reduce postoperative opioid requirements measured in the PACU and in the first 24 hours following surgery.

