#### 5.0 RANDOMIZATION/RECRUITMENT DETAILS (If applicable)

- Randomization groups, how will subjects be randomized:

All subjects who are patients of Drs. [name] and/or [name] and scheduled for kidney stone-related surgery will be potentially recruited.

Part 1: In an initial open run-in period, six patients will be recruited and given a dose of 10 mg baclofen preoperatively so that potential side effects can be assessed in an unblinded fashion.

Part 2: After that, patients will be identified and initially stratified into two groups based on preoperative opioid use. If daily using >30 Oral Morphine Equivalents (OMEs) for more than one month they will be designated as Opioid Tolerant. Otherwise, they will be included in the Opioid Naïve group. These two groups will then be each randomized (envelope assignment) into receiving either baclofen (10 mg, p.o. x 1) or placebo as a preoperative medication such that there will be 4 groups of 20 patients identified:

Group 1: Opioid Tolerant – baclofen

Group 2: Opioid Tolerant – placebo

Group 3: Opioid Naïve – baclofen

Group 4: Opioid Naïve - placebo

- Blinded  Yes  No (Single  Double  please check box).

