#### 6.0 STUDY INTERVENTIONS/PROCEDURES

- Study design: Placebo-controlled double-blind
- Comparison groups (for prospective and clinical trials only).

Placebo treated individuals

- Timeline of interventions (for prospective and clinical trials only).

Patients will be recruited preoperatively by Drs. [name] and [name], in addition to anesthesiology-related personnel in the KPAC. Informed consent will be obtained at that time. On the Day of Surgery, subjects will be contacted by study personnel in the Preoperative Holding area to confirm patient participation and then a randomization envelope containing a single dose of either baclofen or placebo will be opened (Groups 1&2 intermixed; Groups 3&4 intermixed; envelopes will be prepared ahead of time by a different investigator according to a randomization table). Subjects will then consume the pill in the envelope and this will be recorded. Patients will then be treated intraoperatively and postoperatively according to the standard of care associated with these surgeries but with an attempt to utilize consistent doses of intraoperative opioids other agents across groups and standardized PACU orders. After discharge from the

PACU patients' pain will be treated with PCA morphine. Notably, the treating anesthesiologist and all PACU personnel will be blinded to the drug that was administered preoperatively. The total use of analgesics, measures of any other side effects (nausea, excessive sedation) will be recorded for 24 hours.

- **Measured Outcomes:**
  - a. Primary outcomes: Postoperative opioid consumption (measured as OMEs)
  - b. Secondary outcomes: Incidence of nausea/vomiting; excessive sedation per patient self assessment; any other untoward events

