## **9.0 STATISTICAL CONSIDERATIONS**

- Original Plan for Statistical Analysis : Data analysis will be by ANOVA analysis using Tukey's HSD for post-hoc analysis for primary outcome data and Fishers Exact test for categorical incidence data. A mid-point analysis was proposed after the study of 40 subjects.

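### Section 9.0 leaves the ANOVA model unspecified and names neither a pooled baclofen effect nor a drug-by-stratum contrast, so separate Tukey verdicts in the two opioid strata could be read as a difference between them

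*Combined protocol and SAP*

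**What the plan says.** Section 1.0 states that "patients will be stratified into those which would be expected to be opioid tolerant" or opioid naïve. The reason it gives is that prior opioid use is common in this population, "which would be expected to alter postoperative pain medication requirements". That is a reason about the level of need, not about a different response to baclofen. Section 5.0 defines the strata ("If daily using >30 Oral Morphine Equivalents (OMEs) for more than one month they will be designated as Opioid Tolerant"; everyone else is opioid naïve) and the allocation: "These two groups will then be each randomized (envelope assignment) into receiving either baclofen (10 mg, p.o. x 1) or placebo", "such that there will be 4 groups of 20 patients identified". Groups 1 and 2 are tolerant patients on baclofen and placebo; Groups 3 and 4 are naïve patients on baclofen and placebo.

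The hypothesis in Section 3.0 is a single overall one: baclofen "will reduce postoperative opioid requirements measured in the PACU and in the first 24 hours following surgery".

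For the primary outcome, Section 9.0 says only "ANOVA analysis using Tukey's HSD for post-hoc analysis for primary outcome data". It gives no model, factors, interaction term, pooled comparison or list of pairs of interest. No alpha, effect size, SD or power appears anywhere in the document.

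**The concern.** Tukey's HSD compares pairs of means, and the design labels exactly four groups. The natural output is therefore six pairwise comparisons. Two of them are baclofen against placebo within a stratum, and neither answers the overall question in Section 3.0. Nothing named in the plan tests whether the two within-stratum effects differ.

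One stratum significant and the other not is a weak basis for saying that the effects differ. Each verdict rests on 20 against 20, and when power per stratum is intermediate the two verdicts will often split even if baclofen works equally well in both. With no rule set in advance, such a split could be reported as benefit confined to tolerant or to naïve patients. Section 7.0 foresees a follow-up study of longer baclofen use, so what this trial says about each kind of patient may carry forward.

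**Working it through.** The plan states no power or sample-size figure, so there is none to reproduce; 80 is simply 4 × 20.

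**Inputs from the documents.** Four groups of 20, randomised within stratum (Section 5.0). Error df = 80 − 4 = 76.

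**Assumptions, because the documents are silent.** Two-sided familywise alpha of 0.05; normal outcomes; equal SD in all groups; no dropout; no allowance for the mid-point look; the same true effect of d SD in both strata, with d varied from 0 to 1.5.

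**Step 1: Tukey threshold.** Critical |t| = q(0.95; 4, 76)/√2 = 2.627.

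**Step 2: power in one stratum.** The SE of a 20 v 20 difference is √(2/20) = 0.316 SD, so the noncentrality is d/0.316 = d√10. The noncentral t with 76 df gives the power p.

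**Step 3: exactly one stratum significant.** This is roughly 2p(1 − p). At d = 0.8, for example, 2 × 0.466 × 0.534 = 0.498. The two tests share one error variance, which lowers this slightly; simulation with 200,000 trials per setting gives 0.484.

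| True effect in both strata (SD) | Power per stratum (Tukey) | Exactly one stratum significant | Interaction contrast significant |
|---|---|---|---|
| 0 | 1% | 2% | 5% |
| 0.2 | 3% | 5% | 5% |
| 0.5 | 16% | 26% | 5% |
| 0.6 | 24% | 36% | 5% |
| 0.8 | 47% | 48% | 5% |
| 1.0 | 70% | 41% | 5% |
| 1.2 | 88% | 21% | 5% |
| 1.5 | 98% | 4% | 5% |

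The last column is the chosen alpha, as it must be when the true effects are equal. What it shows is that this error rate does not depend on d, whereas the rate of split verdicts does.

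**Step 4: sensitivity.** Requiring a significant overall F-test first changes the split rate by about 1 point or less. A shift in level between strata leaves it essentially unchanged. If the tolerant stratum's SD is twice the naïve stratum's, with d in naïve-SD units, the rate falls to 11%, 15%, 25% and 37% at 0.5, 0.6, 0.8 and 1.0 SD.

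**Step 5: what the missing contrasts can deliver.**
- Pooled baclofen effect: SE = √(2/40) = 0.224 SD. At two-sided 0.05, power is about 60%, 75%, 94% and 99% at 0.5, 0.6, 0.8 and 1.0 SD. Tukey within one stratum gives 16%, 24%, 47% and 70%.
- Interaction, (Group 1 − Group 2) − (Group 3 − Group 4): SE = √(4/20) = 0.447 SD, twice the pooled SE. The 95% interval has half-width 1.992 × 0.447 = 0.89 SD. The difference detectable with 80% power is (1.992 + 0.846) × 0.447 = 1.27 SD. If baclofen works in one stratum only, power (noncentral t, noncentrality d/0.447) is about 20%, 42% and 60% at 0.5, 0.8 and 1.0 SD.

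**The case against.** The strongest reply is that Section 9.0 is vague rather than wrong. It does not say that the ANOVA is one-way, and a two-way ANOVA with an interaction term is not excluded. A reader might infer that the plan commits the trial to separate stratum verdicts and rejects an interaction test; the text does not support that. The fault is under-specification. It still needs mending, because silence leaves the model to be chosen after the data are seen.

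Second, the hypothesis is overall and no section announces a stratum-specific claim. Section 7.0 describes the follow-up study without choosing between tolerant and naïve patients. That a split verdict would misdirect it is therefore a possibility, not something the documents show. This part of the reply stands. It also means that the absent pooled contrast matters at least as much as the absent interaction.

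Third, the size rests on assumptions. A reader might look at the middle of the table and infer that more than a third of trials would show a split whenever the true effects are equal. The documents give no effect size or SD, and over 0 to 1.5 SD the rate runs from 2% to 48%. Equal SDs are also doubtful, since Section 1.0 expects prior opioid use to alter requirements. Small effects are no real reassurance, though: splits are rare there mainly because neither stratum is usually significant. Among trials with at least one significant stratum, the share that split is 0.256/(0.256 + 0.027), about 90%, at 0.5 SD and 0.484/(0.484 + 0.224) = 68% at 0.8 SD.

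Fourth, a reader might infer that any observed split would be mostly chance. The calculation sets the true difference to zero, so every split in it is chance by construction. It cannot say what share of real splits would be.

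**Conclusion.** The point holds as a gap in specification that should be closed. Section 9.0 does not define the ANOVA model, does not name the pooled comparison that would answer the stated hypothesis, and does not name the contrast that would show whether the strata differ. The one follow-up it names, applied to the four groups, gives a separate verdict per stratum. With normal outcomes, equal SDs and a common true effect, those verdicts split in anything from 2% to about 48% of trials. The rate is highest near 0.8 SD and lower at 0.5 to 1.0 SD (naïve-SD units) if tolerant patients vary more. A direct contrast holds the false-difference rate at 5% whatever the common effect. The case for the change does not depend on any one of these percentages.

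**What to change.** State the following in Section 9.0:

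- The primary analysis is a two-way ANOVA with factors drug and opioid stratum and their interaction.
- The overall hypothesis is judged by the baclofen effect pooled over strata, the average of (Group 1 − Group 2) and (Group 3 − Group 4), with its 95% confidence interval.
- Any difference between strata is judged only by the contrast (Group 1 − Group 2) − (Group 3 − Group 4), with its 95% confidence interval, on the OME scale. A ratio-scale version is a sensitivity analysis. It is needed because the same proportional reduction r gives OME differences of r times each stratum's placebo mean, which are unequal when those means differ.
- Stratum-specific Tukey results are descriptive. No benefit confined to one stratum is claimed unless the interaction interval excludes zero.

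This needs a few sentences and two contrasts from data already being collected; recruitment, treatment and blinding are untouched. The real cost is restraint. With 80% power only for a difference of about 1.27 SD, the interaction interval will be wide, and a genuine stratum-specific effect will often not be claimable. The report should then say that the trial could not tell whether the strata differ, not that they respond alike.

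### Section 9 does not say which groups Fisher's exact test compares for the side-effect outcomes, and does not carry the opioid-use stratification into that analysis

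*Combined protocol and SAP*

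**What the plan says.** Section 5.0 sets the strata first: "patients will be identified and initially stratified into two groups based on preoperative opioid use". Treatment is then allocated inside each: "These two groups will then be each randomized (envelope assignment) into receiving either baclofen (10 mg, p.o. x 1) or placebo", "such that there will be 4 groups of 20 patients identified". Section 6.0 confirms one set of envelopes per stratum: "Groups 1&2 intermixed; Groups 3&4 intermixed".

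Section 6.0 lists the outcomes concerned: "Secondary outcomes: Incidence of nausea/vomiting; excessive sedation per patient self assessment; any other untoward events". Section 9.0 gives their analysis in one phrase, "Fishers Exact test for categorical incidence data", in the same sentence that assigns ANOVA with Tukey's HSD to the primary outcome. It also mentions a mid-point analysis after 40 subjects.

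For the categorical outcomes there is no table layout, stratified method, effect estimate, confidence interval, alpha, expected event rate or power.

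**The concern.** An ordinary Fisher's exact test has no term for a stratum, so how the strata enter depends on the table chosen, and the plan does not choose one. Tukey's HSD serves a purpose only with more than two groups, so a reader could fairly assume that Fisher's test is also meant to run over the four groups. That version asks whether any groups differ, including Tolerant from Naïve, which is not a drug effect. Section 1.0 stratifies because prior opioid use is expected to change postoperative medication needs. Rates of nausea or sedation could plausibly differ between strata for the same reason.

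These are the trial's only planned side-effect comparisons. Section 8.0 lists mild sedation among baclofen's most frequent effects, Section 6.0 has patients on PCA morphine after the PACU, and Section 7.0 looks ahead to a follow-up study informed by safety and tolerability. A layout left open can also be picked after the data are seen, and there is a mid-point look.

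**Working it through.** **Inputs from the documents.** Four groups of 20 (Section 5.0): 4 × 20 = 80 in total, 40 baclofen v 40 placebo, 20 v 20 within each stratum. The mid-point of 40 is half of 80. There is no power or sample-size calculation to reproduce.

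**Assumptions.** Two-sided alpha 0.05, no dropout, and the event rates shown, since the plan gives none. All probabilities come from full enumeration of the binomial outcomes (21⁴ combinations for the four groups).

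**Tests compared**
- Four-group Fisher (Freeman-Halton): given the total number of events m, each table has probability ∏C(20, x_g)/C(80, m). The p-value sums all tables no more probable than the one observed.
- Pooled Fisher: one 40 v 40 table.
- Exact stratified: S is the total of baclofen events over both strata. Given the stratum totals m₁ and m₂, S follows the convolution of two hypergeometric distributions.
- Cochran-Mantel-Haenszel (CMH), no continuity correction: X² = (S − (m₁ + m₂)/2)²/V, with V = Σ 20·20·m_k(40 − m_k)/(40²·39), referred to 3.84.

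**Step 1. No baclofen effect: probability of a significant result**

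| Tolerant / Naïve rate | Four-group Fisher | Pooled Fisher | Exact stratified | CMH |
|---|---|---|---|---|
| 30% / 30% | 0.047 | 0.028 | 0.029 | 0.049 |
| 20% / 30% | 0.110 | 0.028 | 0.029 | 0.050 |
| 20% / 40% | 0.328 | 0.025 | 0.029 | 0.049 |
| 10% / 30% | 0.423 | 0.024 | 0.026 | 0.050 |
| 10% / 40% | 0.757 | 0.020 | 0.027 | 0.050 |

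Only the four-group layout reacts to the strata.

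**Step 2. Separate 20 v 20 pairs.** Power per pair is 0.242 for 10% v 30% and 0.192 for 20% v 40%. With 1 event on placebo, significance needs 7 on baclofen. Both pairs would be run, so for 10% v 30% in each stratum the chance that at least one is significant is 1 − (1 − 0.242)² = 1 − 0.758² ≈ 0.42. With no drug effect, the chance that either pair is significant is 0.036 (strata at 10% and 30%) or 0.046 (20% and 40%).

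**Step 3. One comparison using all 80 patients: power**

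| Placebo v baclofen rate | Pooled Fisher | Exact stratified | CMH |
|---|---|---|---|
| 10% v 30% in both strata | 0.534 | 0.534 | 0.632 |
| 20% v 40% in both strata | 0.408 | 0.411 | 0.499 |
| 10% v 30% in one, 50% v 70% in the other | 0.353 | 0.430 | 0.519 |

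**Step 4. What sample size still limits.** The usual two-proportion formula at 80% power needs, for 10% v 30%,

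n = [1.96·√(2·0.2·0.8) + 0.8416·√(0.1·0.9 + 0.3·0.7)]²/0.2² = (1.109 + 0.461)²/0.04 ≈ 62 per arm,

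or 72 with continuity correction. The trial has 40 per arm.

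**The case against.** A reader might infer that the plan chose a test that ignores the strata. The documents do not support that: Section 9.0 is silent on layout. Comparing Group 1 with 2 and Group 3 with 4 would respect the strata fully and would match the envelope sets. Given the reason for stratifying in Section 1.0, separate comparisons are a legitimate choice. What they lack is any combined answer to the drug question.

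A reader might also infer that the planned analysis will raise false alarms. That follows only under the four-group layout, only if stratum rates differ, and only if a significant result is read as a baclofen effect. A four-group test that detects a real Tolerant v Naïve difference has rejected its own null correctly, and nothing in the plan says how such a result would be interpreted. At equal rates its error rate is 5%, and at 20% v 30% it is 11%.

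Third, setting 24% against 63% would overstate what stratifying gains. Most of the gain comes from putting all 80 patients into one test. The pooled Fisher test reaches 53% without stratifying, the same as the exact stratified test when the strata are alike. The fairer figure for the within-stratum pairs is 42%.

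Finally, these are secondary outcomes with no power claimed, and no rewording of Section 9.0 supplies the missing sample size. All of this stands. It narrows the point but does not remove it: the comparison is still unnamed, and its properties depend heavily on the layout.

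**Conclusion.** The point holds as an unspecified comparison that leaves the stratified randomisation out of the analysis. It does not hold as proof that the wrong test was chosen. Depending on a layout that the plan leaves open, the probability of a significant result with no drug effect runs from about 2% (pooled) to 42% (four groups, strata at 10% and 30%), and higher for wider gaps. Pooling costs little when the strata are alike. When they differ widely it costs more: 35% power against 43% (exact stratified) and 52% (CMH).

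A stratified test keeps its type I error at or below about 5% in every scenario examined, and its power matches or exceeds that of the pooled test. Even so, a rise from 10% to 30% would be detected only 53% to 63% of the time, so a non-significant result should not be read as evidence of safety. The sizes rest on assumed event rates, alpha 0.05 and complete data. The silence of Section 9.0 on the comparison does not depend on those assumptions. The change should be made, but the point is one of specification for secondary outcomes.

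**What to change.** In Section 9.0, name one baclofen v placebo comparison for each categorical outcome, stratified by opioid tolerance: a Cochran-Mantel-Haenszel test, or the exact stratified test when events are few, with the criterion for switching fixed in advance. Report the stratum-adjusted risk difference with its 95% confidence interval, so that the reader sees how large an excess remains compatible with the data. Show the counts in each of the four groups descriptively.

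The cost is a sentence or two, with no new data or patients. The downsides are that stratum-specific p-values become descriptive, and that a test for a common effect can hide opposite effects in the two strata. The four-group counts should therefore always appear beside it.

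### The analysis after 40 of 80 patients has no alpha or boundary, and the deciding comparison is not named, so the error rate of the primary claim cannot be stated from the plan

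*Combined protocol and SAP*

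**What the plan says.** All references are to the combined protocol and SAP.

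- **Section 9.0, interim look.** "A mid-point analysis was proposed after the study of 40 subjects". This is all the document says about the look. It gives no purpose, significance level, boundary or change to the final test. The section is labelled as the original plan and this sentence is in the past tense, so it is also unclear whether the look still stands.
- **Section 9.0, primary analysis.** "Data analysis will be by ANOVA analysis using Tukey's HSD for post-hoc analysis for primary outcome data". The comparison that decides success is not named.
- **Section 5.0.** Patients are stratified by prior opioid use and randomised to baclofen or placebo within each stratum, so that "there will be 4 groups of 20 patients identified".
- **Section 6.0, Measured Outcomes.** "Primary outcomes: Postoperative opioid consumption (measured as OMEs", with no time window. The same section says: "The total use of analgesics, measures of any other side effects (nausea, excessive sedation) will be recorded for 24 hours".
- **Section 1.0.** The aim is the "effect of a single preoperative dose of baclofen on pain treated in the first 24 hours after kidney stone-related surgeries".
- **Section 3.0.** The hypothesis is that baclofen "will reduce postoperative opioid requirements measured in the PACU and in the first 24 hours following surgery".

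Taken together, Sections 1, 3 and 6 imply a 24-hour window. The role of the PACU in the primary outcome is not stated.

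**The concern.** Three choices that fix the error rate are left open: whether the 40-patient look can support a claim, which comparison decides, and which window is primary. Each could still be settled after data have been seen. Tukey's HSD adjusts for comparing pairs of groups. It does not adjust for looking twice or for a second window.

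A reader of a positive result could not tell whether it came from the planned test, and could not attach an error rate to it. The unnamed comparison also affects power. The drug main effect uses all 80 patients, whereas a within-stratum Tukey pair uses 40 and pays a multiplicity penalty.

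**Working it through.** **The plan's own figures.** 4 × 20 = 80 randomised, and 40/80 = 0.50, which agrees with the description of the look as the mid-point. The sample size itself cannot be reproduced, because no alpha, power, effect size or SD is given.

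**Assumptions.** Two-sided 5% at each look; an efficacy claim possible at either look; information fraction 0.50; 10 per group at the look and 20 at the end.

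**1. Drug main effect at both looks.**
- Overall error = 1 − P(|Z1| < c and |Z2| < c), with c = 1.960 and correlation √0.50 = 0.707 between the two statistics.
- Result: 0.083. Simulated t tests (36 and 76 df) also give 0.083.
- Counting only results in baclofen's favour, it is 4.2% against a nominal 2.5%.
- If the strata fill unevenly and the information fraction at the look is only 0.32, it is 8.9%.

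**2. No claim at 40.** One named test in one window at the end: 5%.

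**3. Tukey, the two baclofen-placebo pairs only.** Four groups, pooled variance, studentized-range critical values, simulated:

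| Tolerant SD ÷ naive SD (assumed) | One look | Two looks |
|---|---|---|
| 1 | 2.1% | 3.7% |
| 2 | 4.2% | about 7% |
| 3 | 5.6% | about 9% |

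The documents give no SDs. Section 1.0 expects prior opioid use to alter postoperative requirements, so unequal spread is plausible.

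**4. Power of the two candidate tests at 80 patients** (equal SDs, same effect in both strata, SD = 1).
- Main effect, 40 v 40: SE = √(1/40 + 1/40) = 0.224. For 80% power the difference is 2.80 × 0.224 = 0.626.
- One stratum pair, 20 v 20: SE = √(1/20 + 1/20) = 0.316, so the expected statistic is 0.626/0.316 = 1.98.
- Tukey critical value: 3.715/√2 = 2.63. Power for one pair is P(Z > 2.63 − 1.98) ≈ 0.26. For at least one of two it is 1 − 0.74² ≈ 0.45. Simulation gives about 46%.

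**5. Boundaries that hold the error.**
- p<0.001 at 40, then 5%: overall 5.0%.
- O'Brien-Fleming, about 0.0052 then 0.048: overall 5.0%.

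**6. Price of a boundary.** With 80% power at 80 patients (assumption), the drift at 40 is 2.80/√2 = 1.98. The chance of a claim at 40 is:
- P(Z > 1.96 − 1.98) = 51% at p<0.05;
- P(Z > 2.80 − 1.98) = 21% with O'Brien-Fleming;
- P(Z > 3.29 − 1.98) = 10% at p<0.001.

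**The case against.** The strongest reply is that the plan never says a claim can be made at 40. A look for safety, variance or non-binding futility adds no error. The only comparison procedure named beyond ANOVA is Tukey's HSD, and with equal SDs its baclofen-placebo pairs stay at 3.7% even over two looks. The study is also small and is meant to lead to a follow-up study (Section 7.0), which limits the harm. These points stand as far as they go. They show that the plan may not be inflated, but not that its error rate is known. The 3.7% also depends on equal spread in the two strata.

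A reader might infer three stronger things that the documents do not support.

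- **That the trial's error is 8.3% rather than 5%.** This needs a 5% alpha, a claim allowed at 40, and the main effect as the test. None of these is stated.
- **That success in either the PACU or the 24-hour window would count, inflating the error further.** Section 3.0 joins the two windows with an and, Sections 1.0 and 6.0 point to 24 hours, and 24-hour use probably includes PACU use, so the windows would be correlated. The gap is the PACU's undefined role, not a demonstrated second chance to win.
- **That the six open-label patients might count towards the 40.** Section 5.0 sets them apart ("In an initial open run-in period, six patients will be recruited"), and 40 is the mid-point only of the 80 randomised.

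**Conclusion.** The concern holds as an omission: the error rate of the primary claim cannot be derived from Section 9.0. Depending on how the gaps are filled, it is 5% (no claim at 40, one named test in one window), about 8.3% (main effect at two-sided 5% at both looks), about 3.7% (Tukey baclofen-placebo pairs at both looks, equal SDs), or about 7-9% (the same pairs with a tolerant SD 2-3 times the naive SD). The alpha, the possibility of an early claim and the SD ratios are assumptions. None of these figures is a property of the plan as written.

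Naming the deciding test also matters for power: about 46% for the Tukey pairs against 80% for the main effect, if SDs are equal and the effect is the same in both strata. The change should be made. It is cheap, and it decides whether a positive result can be interpreted.

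**What to change.** Settle these before the 40-patient look.

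**Section 9.0**
1. Make the baclofen-versus-placebo main effect, from an ANOVA with opioid-tolerance stratum as a factor, the deciding test, and state its alpha. Tukey comparisons become supportive.
2. Say whether the look is kept and what it is for. Either state that it makes no efficacy claim, or, if an early claim is wanted, give a boundary that keeps the overall error near 5%: for example p<0.001 then 5%, or O'Brien-Fleming (about 0.0052 then 0.048).

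**Section 6.0**

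3. Name one primary window. The choice is the sponsor's; 0-24 hours is the one the documents most consistently imply. Test the PACU window only if the first is significant, with the same boundary if the look can make claims.

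If the look has already been done, say so and report what was tested and how.

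**Cost.** A few sentences in two sections. No new patients or data are needed, since Section 3.0 already plans measurement in both windows. The price is that an early claim is harder (a 51% chance at p<0.05 falls to 21% or 10% under the two boundaries, at 80% final power), and neither the PACU window nor a Tukey pair can carry the primary claim alone.
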